8. HANDLING OF MISSING DATA

Efficacy endpoints will be summarized by visit using observed cases (OC) and last observation carried forward (LOCF) methods as appropriate. Baseline values will not be carried forward.

Imputation of Start and End Dates of Adverse Event (AE)

To calculate duration of Adverse Events, the following rules will be used where applicable to impute partial or completely missing start dates or end dates:

- If only the day is missing for a start date, the 1st of the month will be imputed. If the new estimated date falls before the Visit 1 date, while the known month and year match the month and year of the Visit 1 date, the date of Visit 1 will be used as the new estimated date.
- If only the day is missing for an end date, the last day of the month will be imputed. If the new estimated date falls after the date of last study visit, the date of last study visit will be used as the new estimated date.
- If both the day and the month are missing for a start date or end date, no imputation will be used, and the duration will not be calculated.
- If the start date or end date is completely missing, duration will not be calculated.

For AEs ongoing at the end of pivotal studies, duration will be computed using the DMVT-505-3003 visit 1 date as the AE start date.

If relationship of AE to treatment is missing, the event will be conservatively considered as being related to study drug. Missing AE severity will be imputed to the highest severity level (most severe). Through the data cleaning process, all attempts will be made to avoid missing values for relationship and severity.

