10. DATA CONVENTIONS FOR ANALYSIS

10.1 General Statistical Principles

The study efficacy and safety results will be summarized descriptively. There will be no statistical testing.

All observed and derived variables (e.g., change from baseline, percentage change from baseline, and response status) that are summarized will be presented in by-subject listings. Unless otherwise noted, the data will be sorted by DB treatment group and subject number and then by date within subject number.

For categorical parameters, the number and percentage of subjects in each category will be presented. The denominators for percentages will be the number of subjects appropriate for the purpose. For continuous parameters, descriptive statistics will include number of subjects, mean, standard deviation (SD), median, minimum, and maximum.

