11.11 Safety Analysis

All safety parameters will be summarized over the ITT population of all enrolled subjects, overall and by DB treatment group.

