11.11.1 Adverse Events

AE terms will be coded using Medical Dictionary for Regulatory Activities (MedDRA) dictionary. All AEs reported in current study are considered as treatment-emergent AE (TEAE) except for those AEs ongoing at the end of pivotal studies but resolved prior to the Visit 1 date in the extension study.

All TEAEs will be listed by subject, detailing the verbatim term given by the investigator, the preferred term (PT), system organ class (SOC), onset date and time, end date and time, ongoing at the end of pivotal studies (Y/N), duration (days), CTCAE grade, outcome, relationship to study drug, action taken with study drug, other action taken to treat the event, AE of special interest (Y/N), seriousness and criteria for seriousness.

AEs resolved prior to the Visit 1 date, Serious TEAEs (STEAEs), TEAEs leading to study discontinuation and TEAEs related to study drug will also be listed separately. The following adverse events of special interest (AESIs) will be identified and listed separately: contact dermatitis, folliculitis, and headache.

The number and percent of subjects with TEAEs will be summarized as incidence rates of:

- Any TEAE
- Any TEAE Excluding Those Ongoing at the end of the Pivotal Studies
- Any TEAE Ongoing at the end of the Pivotal Studies
- Any treatment-emergent AESIs
- Any treatment-emergent AESIs Excluding Those Ongoing at the end of the Pivotal Studies
- Any treatment-emergent AESIs Ongoing at the end of the Pivotal Studies
- Any treatment-related TEAE
- Any TEAE leading to study drug discontinuation
- Any TEAE leading to study discontinuation
- Any serious TEAE

- Death
- Treatment-related Serious TEAE
- Serious TEAE leading to study drug discontinuation
- Serious TEAE leading to study discontinuation
- TEAE (COVID-19)

Individual PTs will be summarized by SOC in alphabetical order and PT in descending order of frequency for the following subsets and subgroupings:

- All TEAEs
- All TEAEs by maximum CTCAE grade
- All TEAEs by maximum causality (not related, related) to the study drug
- All TEAEs Excluding Those Ongoing at the End of the Pivotal Studies
- All TEAEs ongoing at the end of the pivotal studies
- All treatment-related TEAEs
- All TEAEs leading to study discontinuation
- All TEAEs leading to study drug discontinuation
- All serious TEAEs

All TEAEs and all serious TEAEs will also be summarized by SOC (alphabetical order) and PT (descending order) for the following subgroups:

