- Age (<65 and \geq 65 years old)
- Sex
- Race (White, Other)

Furthermore, TEAEs will be categorized by day of onset among the following 4 categories:

- \leq 12 weeks
- >12 to \leq 24 weeks
- >24 to \leq 40 weeks
- >40 weeks.

For each of these categories, TEAEs will be summarized by SOC in alphabetical order and PT in descending order of frequency. TEAEs ongoing at the end of the pivotal studies will be considered in the first category (i.e. day of onset \leq 12 weeks).

At each level of summarization, a subject will be counted once if he/she reported one or more events. The severity of TEAEs and relationship to study drug will be summarized in a similar

manner. For summaries of relationship to study drug, a subject will be classified according to the closest relationship. For summaries of TEAE CTCAE grade, a subject will be classified according to the worst grade.

For AESIs, summarization will be more extensive, reflecting the more detailed information collected. Information summarized will include number of events per subject, earliest onset day, duration (in days), causality, grade and seriousness of AESIs, outcome, actions taken, assorted physical characteristics of the AESIs, and demographic/baseline characteristics and PGA status of the subjects experiencing them. Each type of AESI will be summarized separately. If a subject has more than one treatment-emergent occurrence of an AESI, the subject's maximum duration, highest levels of causality and seriousness, maximum grade and generally the most extreme level of each characteristic will be summarized. If an AESI was ongoing at end of study (EOS), it will not be included in the duration summary. AESIs ongoing at the end of pivotal studies will also be included in the summary.

A Kaplan-Meier figure will be generated for each AESI of time to first event for events starting during the study. Subjects not experiencing the AESI will be censored at the date of study completion or discontinuation. AESIs ongoing at the end of pivotal studies will not be included.

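### The SAP's tables of TEAEs by onset period put AEs carried over from the pivotal studies in the ≤12-week row, which overstates early new onsets; the per-period denominator also needs stating

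*SAP*

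**What the plan says.** SAP section 11.11.1 states that "TEAEs will be categorized by day of onset among the following 4 categories", with cut-points at 12, 24 and 40 weeks. Each category is then summarized by SOC and PT, and a subject counts once per level. For AEs carried over from the parent trials the rule is that "TEAEs ongoing at the end of the pivotal studies will be considered in the first category". They reach the table because the same section treats every AE reported in the extension as treatment-emergent unless it resolved before Visit 1. SAP section 10.3 sets Day 1 at Visit 1, which is also the last pivotal visit.

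Elsewhere the SAP handles these events in several ways:
- Section 8: "For AEs ongoing at the end of pivotal studies, duration will be computed using the DMVT-505-3003 visit 1 date as the AE start date".
- Section 11.11.1, main AESI summary: "AESIs ongoing at the end of pivotal studies will also be included in the summary".
- Section 11.11.1, AESI Kaplan-Meier figures: "AESIs ongoing at the end of pivotal studies will not be included".
- Section 11.11.1, whole-study SOC/PT tables: one for all TEAEs, one headed "All TEAEs Excluding Those Ongoing at the End of the Pivotal Studies", and one for carried-over events alone. The TEAE listing has a yes/no flag for them.

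On denominators, section 11.11 says "All safety parameters will be summarized over the ITT population of all enrolled subjects, overall and by DB treatment group", and section 10.1 says "The denominators for percentages will be the number of subjects appropriate for the purpose". The available text gives no per-period number at risk or person-time. Section 15, the outline of tables, is only a heading there.

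**The concern.** A table organized by onset should show when new events begin. Placing an AE that started in the pivotal study in the ≤12-week row follows the Visit 1 convention that section 8 uses for duration, but Visit 1 is not when the AE began. The rule works one way only: it can add subjects to the first row and never to a later one.

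Long-term safety and tolerability is the first study objective, and these are the only tables of all TEAEs over time that the available SAP text describes. A reader who compares rows could conclude that AEs become less frequent with continued use when part or all of the fall comes from the carry-over rule.

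A lesser issue makes the rows harder to compare. The periods last 12, 12, 16 and about 4 weeks, and the plan expects heavy attrition, so a percentage without a stated denominator cannot be read across rows.

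**Working it through.** **Inputs from the documents.** SAP section 6 gives about 850 enrolled and about 300 completing, an implied discontinuation of 1 − 300/850 = 64.7%. Period lengths follow from section 11.11.1 and the 44-week participation. No figure is stated for the onset tables, so there is none to reproduce. **Assumed, because the documents are silent:** the new-event rate h, the carry-over share p and the timing of dropout.

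**1. Carry-over alone, no dropout.** The share with a new event in 12 weeks is q = 1 − exp(−12h). At h = 0.01 per week, q = 1 − exp(−0.12) = 11.3%, so rows 1 and 2 should be equal. If carry-over is independent of new events, row 1 becomes 1 − (1 − p)(1 − q).

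| p | Row 1 | Row 2 | Ratio |
|---|---|---|---|
| 0% | 11.3% | 11.3% | 1.00 |
| 2% | 13.1% | 11.3% | 1.16 |
| 5% | 15.7% | 11.3% | 1.39 |
| 10% | 20.2% | 11.3% | 1.78 |

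At p = 5% the ratio is 3.06 for h = 0.002 and 1.08 for h = 0.04, so the distortion is larger where new events are rarer. If the same subjects tend to have both kinds of event, the inflation is smaller, because a subject counts once per level. It is nil for any SOC or PT with no carried-over event.

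**2. What the planned whole-study tables recover.** Let T be the share with any TEAE, A the share with any TEAE excluding carry-over, and C the share with a carried-over AE. Subjects in row 1 only through carry-over lie between T − A and C. Take h = 0.01, p = 5%, all enrolled subjects as denominator and constant dropout d = ln(850/300)/40 = 0.02604 per week.
- True new-onset row 1: h/(h + d) × [1 − exp(−12(h + d))] = 9.7%.
- Printed row 1: 1 − 0.95 × (1 − 0.0974) = 14.3%.
- T = 26.0%, A = 22.1%, T − A = 3.89%, C = 5%.
- Recoverable range: 14.26 − 5.00 = 9.3% to 14.26 − 3.89 = 10.4%.

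**3. Denominator, no carry-over, h = 0.01.** Under constant dropout, 850, 622, 455 and 300 subjects are in study at the start of the four periods. Expected subjects with a new event are 82.8, 60.6, 55.3 and 11.8.

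| Measure | ≤12 | >12–24 | >24–40 | >40 |
|---|---|---|---|---|
| % of 850 | 9.7 | 7.1 | 6.5 | 1.4 |
| % of number at period start | 9.7 | 9.7 | 12.2 | 3.9 |
| Person-years in study | 167.9 | 122.8 | 114.1 | 23.0 |
| Subjects per 100 person-years in study | 49.3 | 49.3 | 48.5 | 51.1 |
| Subjects per 100 person-years to first event | 52.2 | 52.2 | 52.2 | 52.2 |

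The true rate is flat at 0.01 × 52.18 × 100 = 52.2 per 100 person-years. Percentages of 850 fall. Percentages of those at period start rise in the third period only because it is longer. Person-time to first event returns the flat rate.

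The fall depends on when subjects leave. Linear dropout gives 10.2%, 8.0% and 7.2% of 850 in rows 1 to 3. If all loss falls in Weeks 38 to 40, rows 1 and 2 are both 11.3% and row 3 is about 14%, so no decline appears.

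**The case against.** The carry-over rule is disclosed, and the SAP already separates these events: by SOC and PT over the whole study, in the listing flag and in the AESI Kaplan-Meier figures. In the 5% example a reader could recover the new-onset figure to within about one percentage point. The study is descriptive with no testing, and no comparison between periods is planned. Every rate and share above is assumed, and the illustrative ratio at a 5% share runs from 1.08 to 3.06. All of this stands, and it limits the harm. It does not correct the by-period tables themselves, whose first row would still be labelled as onset, and the recovery takes cross-table subtraction that few readers will do.

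On denominators, a reader might infer that the SAP divides every row by all enrolled subjects and so builds in a spurious decline. The documents do not support that. Section 11.11 names an analysis set, section 10.1 leaves room for a per-period denominator, and the content of section 15 is not available. Use of 850 is an inference. Even if it were used, dropout concentrated just before Week 40 would produce no decline.

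**Conclusion.** The carry-over rule is wrong for a table defined by onset: followed as written, it can only overstate new onsets in the ≤12-week row. The direction follows from the text; the size does not. The rise from 11.3% to 13.1%, 15.7% or 20.2% rests on no dropout, 0.01 events per week, shares of 2%, 5% or 10%, and independence.

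A reader might also infer that the SAP's safety analysis as a whole is distorted or that carried-over AEs are hidden. Neither holds: the effect is confined to the onset-period tables, and the separate whole-study tables are sound on this point.

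The denominator issue is secondary. It is an omission in the available text, not a demonstrated bias. The 9.7%, 7.1% and 6.5% pattern is conditional on both constant dropout and all enrolled subjects as denominator. Stating the denominator and adding person-time is still worthwhile, given the plan's own expected fall from about 850 to about 300 and the unequal periods.

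**What to change.** **Main change.** Restrict the onset-period tables to TEAEs not flagged as ongoing when the pivotal study ended, or show the flagged events in a separate row. Keep the existing carry-over table. Let the flag, not the date, decide events starting on Day 1: Day 1 belongs to both studies, and the section 8 imputation can move a partial start date to Visit 1.

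**Secondary change.** For each period and DB group, report the number of subjects in study at its start and new-onset subjects per 100 person-years. Use in-study time for individual PTs (at 0.002 per week it gives 10.3 to 10.4 against a true 10.4) and time to first event for the any-TEAE row. Label it as time in study, not drug exposure, because under protocol section 3.1 treatment stops at PGA 0 and may restart. Footnote that the >40-week row covers mainly the roughly 4-week follow-up, and that in-study time includes subjects who still have an ongoing AE of the same PT.

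**Cost.** A short SAP amendment and some extra table columns; no new data. Late-period figures may look less favourable.

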8.3. Time Period and Frequency for Event Assessment and Follow-up

8.3.1. Adverse Event Reporting

All AEs will be collected from the time of signed informed consent until the final visit.

Any AEs assessed as related to study participation (e.g., protocol-mandated procedures, invasive tests, or change in existing therapy) will be collected from the time a subject consented to participate in the study up to and including any follow-up contact.

All SAEs will be recorded in the eCRF and reported to the Sponsor within 24 hours via email or phone (refer to Medical Monitor/Sponsor Information page for contact information) (see Section 8.4).

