8.3.2. Follow-up of Adverse Events

After the initial AE/SAE report, the Investigator is required to proactively follow each Subject at subsequent visits/contacts. All SAEs and nonserious AEs will be followed until resolution, until the condition stabilizes, until the event is otherwise explained, or until the subject is lost to follow-up.

The Investigator will assess the outcome of each AE using the following criteria:

- **Recovered/Resolved:** The event has improved or subject recuperated.
- **Recovered/Resolved with sequelae:** The subject has recuperated but retained pathological conditions resulting from the prior disease or injury.
- **Recovering/Resolving:** The event is improving.
- **Not recovered/Not resolved:** The event has not improved or subject recuperated.
- **Unknown:** The outcome of the event is not known, not observed, not recorded, or refused
- **Fatal:** Termination of life as an outcome of the AE.

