6. SAMPLE SIZE DETERMINATION

The sample size of this study is based on the ICH E1 guideline on extent of population exposure to assess clinical safety for drugs intended for long-term treatment of non-life-threatening conditions. An estimated 850 subjects who complete Study DMVT-505-3001 or Study DMVT-505-3002 will be enrolled in this study at approximately 100 to 120 study sites in the US and Canada. A high discontinuation rate is anticipated in this long-term extension study. Approximately 300 subjects are expected to complete the study (40 weeks of treatment).

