11.7 Efficacy Endpoints

Efficacy endpoints are as follows:

For subjects entering the study with a PGA score of clear (0):

- Proportion of subjects who experience PGA ≥ 2 at least 1 time during the study.
- Proportion of subjects who never experience PGA ≥ 2 throughout the study.
- Time to first worsening (PGA ≥ 2), defined as days from date of Visit 1 date to the date of first occurrence of PGA ≥ 2 . Subjects who never experience PGA ≥ 2 throughout the study will be censored at the date of their last PGA assessment.

For subjects entering the study with a PGA score ≥ 1 :

- Proportions of subjects who achieve PGA = 0 at least 1 time during the study

• [REDACTED]

• [REDACTED]

[REDACTED]

For subjects entering the study with a PGA score ≥ 2 :

- Proportions of subjects who achieved PGA = 0 or 1 at least 1 time during the study.
- Proportions of subjects who never achieve PGA = 0 or 1 throughout the study.

The following endpoints will be summarized over subjects in ITT population:

- Duration (days) of treatment episodes, defined as time (days) from the date of each PGA ≥ 2 (or PGA ≥ 1 for the first episode) to 1 day before each subsequent treatment success (PGA = 0). The date of the last PGA assessment will be used as the end date for episodes ongoing at the end of the study.

- [REDACTED]
- [REDACTED] \geq [REDACTED]
- [REDACTED]
- [REDACTED]
- [REDACTED]
- [REDACTED] change and percent change from baseline in %BSA affected by visit (OC and LOCF).
- [REDACTED] change and percent change from baseline in PASI score by visit (OC and LOCF)
- [REDACTED] \geq [REDACTED]
- [REDACTED] \geq [REDACTED]
- [REDACTED] \geq [REDACTED]

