11.8 Efficacy Analyses

All efficacy parameters will be summarized over the ITT analysis set overall and by DB treatment group. Summaries of efficacy endpoints by visit will be performed using OC and LOCF methods.

Time to event parameters, such as the time from treatment success to subsequent worsening (PGA ≥ 2) or duration of treatment episode, will be summarized by the Kaplan-Meier product limit method using OC. Median time to event will be estimated. If the median time is not determined, other percentiles will be estimated.

The remaining efficacy endpoints will be summarized descriptively as follows: continuous data will include the mean, SD, minimum, maximum, median, and number of observations; descriptive summary statistics for categorical data will include frequency counts and percentages.

For the following efficacy outcomes:

1. Proportions of subjects who achieve PGA = 0 at least 1 time during the study (for subjects entering the study with a PGA score ≥ 1):
2. Proportions of subjects who experienced PGA ≥ 2 at least 1 time during the study (for subjects entering the study with a PGA score = 0):
3. PGA scores at Week 40 (LOCF)
4. BSA [REDACTED] change from baseline to Week 40 (LOCF)
5. PASI [REDACTED] change from baseline to Week 40 (LOCF)

subgroup analyses will be generated for the following groupings:

- Baseline PGA
- Age (<65 and ≥ 65 years old)
- Sex
- Race (White, Other)
- Baseline % BSA affected – ($<10\%$, $\geq 10\%$)
- Duration of disease (<5 years, 5-10 years, >10 years)
- Country (USA and Canada)

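### Leaving AESIs that are still ongoing at end of study out of the duration summary makes reported AESI duration too short and can understate a subject's longest event

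*SAP*

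**What the plan says.** SAP 11.11.1 lists duration in days among the items summarized for each AESI type, and Protocol 8.1.3 asks sites to collect it. Two rules in SAP 11.11.1 define the row:

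- Unresolved events: "If an AESI was ongoing at end of study (EOS), it will not be included in the duration summary".
- Repeat events: the subject's "maximum duration, highest levels of causality and seriousness, maximum grade and generally the most extreme level of each characteristic will be summarized".

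Outcome belongs to the same AESI summary, and every TEAE is listed with its dates and outcome. The only Kaplan-Meier output for AESIs is time to first event.

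Three other places bear on the row:

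- **Carried-in events.** SAP 8 starts the duration of AEs ongoing from the pivotal studies at Visit 1. SAP 11.11.1 includes such AESIs in the summary.
- **Follow-up.** Protocol 8.3.2 says: "All SAEs and nonserious AEs will be followed until resolution, until the condition stabilizes, until the event is otherwise explained". Protocol 8.3.1 says: "All AEs will be collected from the time of signed informed consent until the final visit". The SAP does not say whether end dates after a subject's exit will be used.
- **End of study.** Protocol 7.8 and SAP 3 define it for the study as a whole (last active subject's Follow-up Visit), not for a subject.

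**The concern.** Whether an event enters the duration row depends on whether it was short enough to finish in time. If remaining follow-up is independent of duration, the chance of being counted can only fall as duration rises. The resolved-only figure is then biased short for any duration distribution.

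The exclusion is worded per event and the summary is per subject. A subject whose only AESI is unresolved has no duration. A subject with a resolved 5-day event and another ongoing from Day 100 to Day 309 (309 − 100 + 1 = 210 days so far) is shown with a maximum of 5 days. That works against the SAP's convention of showing the most extreme level.

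Heavy discontinuation makes this more relevant. SAP 6 expects about 300 of 850 subjects to complete. At stake is how long readers of the safety report believe these reactions last.

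**Working it through.** **No plan figure to reproduce.** The documents give no AESI durations and no count of ongoing events. The only relevant arithmetic is 300/850 = 35.3% completing.

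**Assumptions (not in the documents).** Durations are exponential with mean m, and onset is uniform over T = 309 days (Week 44 is Day 309). Exit has a constant hazard matched to 300/850 at Week 40, h = −ln(300/850)/280 = 0.003719 per day (0.0260 per week), with everyone out at Day 309. End of study is taken as the subject's own exit. End dates are known for f days after exit: (a) f = 0, or (b) f = 28. Protocol 8.3.2 supports some later follow-up; the 28 days are assumed.

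**Formulas.** With a = h + 1/m:

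- share dropped S = (h/a) × (1 − e^(−aT)) / (1 − e^(−hT)) × e^(−f/m)
- mean elapsed time at exit of unresolved events: e = 1/a − T e^(−aT)/(1 − e^(−aT))
- resolved-only mean = [m − S(m + e + f)] / (1 − S)

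**Example, m = 30.** a = 0.003719 + 0.033333 = 0.037053, h/a = 0.1004, 1 − e^(−hT) = 0.6832 and e = 27.0.

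- (a) S = 0.1004/0.6832 = 0.1469; mean = (30 − 0.1469 × 57.0)/0.8531 = 25.35.
- (b) S = 0.1469 × e^(−28/30) = 0.0578; mean = (30 − 0.0578 × 85.0)/0.9422 = 26.63.

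**Event level** (percentages computed before rounding):

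| True mean (days) | (a) dropped | (a) resolved-only mean | (a) too low by | (b) dropped | (b) resolved-only mean | (b) too low by |
|---|---|---|---|---|---|---|
| 7 | 3.7% | 6.74 | 3.8% | 0.1% | 6.98 | 0.3% |
| 14 | 7.2% | 12.96 | 7.4% | 1.0% | 13.59 | 2.9% |
| 30 | 14.7% | 25.35 | 15.5% | 5.8% | 26.63 | 11.2% |
| 60 | 26.7% | 42.38 | 29.4% | 16.7% | 44.65 | 25.6% |

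Later follow-up shrinks the share dropped more than the bias, because the events still dropped are the longest.

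**Sensitivity**, at means 14/30/60:

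- 70% completing: dropped (a) 5.4%, 11.3%, 21.7%; (b) 0.7%, 4.4%, 13.6%.
- Earlier onset (assumed exponential, mean 45 days): dropped (a) 5%, 10%, 19%; (b) 0.7%, 4%, 12%.
- Lognormal durations, mean 30: resolved-only mean in (a) and (b) is 28.8 and 29.1 at CV 0.5, and 20.2 and 21.5 at CV 2.

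**Subject level** (simulation of 600,000 subjects; one event per 309 days, about 1.4 per affected subject, assumed), at means 14/30/60:

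| | (a) | (b) |
|---|---|---|
| True mean maximum | 16.8 / 36.1 / 72.2 | 16.8 / 36.1 / 72.2 |
| Mean maximum as shown | 15.4 / 29.9 / 48.8 | 16.2 / 31.6 / 51.9 |
| Affected subjects with no duration shown | 6% / 12% / 22% | 1% / 5% / 14% |
| Affected subjects whose unresolved event has already outlasted the maximum shown | 2% / 4% / 7% | 0.6% / 3% / 7% |

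**Which maxima are censored.** A subject with a resolved 20-day event and an unresolved 15-day event has a maximum of at least 20 days, not exactly 20. Censoring only when the unresolved event is the longest so far would wrongly treat 2% to 6% of affected subjects as fully observed in (a), and up to 3% in (b). In about half of them the true maximum is longer.

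**Does the fix work?** In the same simulation at m = 60, the true median of the per-subject maximum is about 54 days. The resolved-only median is 37 in (a) and 40 in (b). Kaplan-Meier, censoring every subject with an unresolved event, gives 57 and 55. It slightly overshoots but is far closer.

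**The case against.** The strongest reply is that the SAP states the exclusion openly, nothing is tested, and the duration of resolved events is a legitimate descriptive quantity. Much of this stands.

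- **The loss is partly visible.** Outcome is in the same AESI summary, SAP 10.1 gives every continuous parameter its number of subjects, and listings carry dates and outcome. A reader might infer that the plan hides the loss; it does not. But the row's n cannot reveal subjects with both a resolved and an ongoing event, and no described output corrects the duration. Only the heading of the table outline (SAP 15) is available, so layout cannot be judged.
- **The events may be brief.** Protocol 1.3.1.1 says skin reactions generally subside once exposure stops, and treatment ends by Week 40, leaving completers about four weeks before the Follow-up Visit. The constant-hazard model ignores this. For the two skin AESIs it points towards the range where the loss is small.
- **Follow-up to resolution** (Protocol 8.3.2) would shrink the loss, as (b) shows, if the later dates reach the analysis.

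A reader might also infer that the SAP contradicts itself. It does not. The rule "Subjects not experiencing the AESI will be censored at the date of study completion or discontinuation" concerns subjects who never had the event. For treatment episodes, SAP 11.7 says "The date of the last PGA assessment will be used as the end date for episodes ongoing at the end of the study" without calling them censored, and SAP 11.8 says "duration of treatment episode, will be summarized by the Kaplan-Meier product limit method using OC". A different convention for an efficacy endpoint is not a contradiction; it shows only that the method is already planned.

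**Conclusion.** Wrong as written; minor. The downward direction follows from the rule, given that remaining follow-up is independent of duration. The size does not follow from the documents. Under the assumed model the loss is small at means of one to two weeks (0.1% to 7% of events dropped) and becomes material at about a month or more.

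A reader might infer that the AESI profile as a whole is understated, or that the expected 65% discontinuation (550/850) makes the loss large. The documents support neither. AESI incidence, grade, seriousness and time to first event do not use this rule. Even with 35% completing, short events lose little.

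The undefined subject-level end of study affects the size: if it means the study-level date and follow-up continues to resolution, fewer events are dropped, but the direction is the same. The Visit 1 restart for carried-in AESIs is a separate source of shortening in the same row.

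**What to change.** In SAP 11.11.1:

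1. Replace the exclusion. Keep unresolved AESIs and summarize the per-subject maximum duration by Kaplan-Meier (median and quartiles), using the longest elapsed time over all the subject's occurrences.
2. Treat that maximum as censored ('at least') whenever the subject has any unresolved occurrence.
3. Define end of study for this rule as the subject's own last contact, and use any end date collected later under Protocol 8.3.2.
4. Show the number and percent of subjects with an unresolved AESI beside the duration, and label any resolved-only row 'resolved events only'.
5. Flag, or show separately, AESIs carried in from the pivotal studies, because SAP 8 starts their duration at Visit 1.

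**Cost.** SAP wording and one changed row block per AESI. The dates and outcome are already listed, and Kaplan-Meier is already in use. Reported durations will be longer, and upper quartiles may not be estimable where events are few.

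**Limit.** Kaplan-Meier reduces the bias but may not remove it if AESIs themselves lead to discontinuation. In an event-level simulation with mean 60 days and no later follow-up, events longer than the median added an assumed exit hazard of 1/60 per day. Kaplan-Meier quartiles were 16/34/70 days and resolved-only 9/20/34, against a true 17/42/83. The SAP should state this limit.
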